1.7 Dosing for the Nivolumab Combination with Ipilimumab

Data from CA209016 demonstrated a level of clinical activity, as measured by ORR, for the combination of nivolumab combined with ipilimumab that is substantially greater than that of either nivolumab or ipilimumab monotherapy in mRCC. The dosing regimen including nivolumab 3 mg/kg combined with ipilimumab 1 mg/kg was chosen because it exhibits similar clinical activity than nivolumab 1 mg/kg combined with ipilimumab 3 mg/kg along with a more favorable safety profile.^{17,18}

1.8 Dosing for the Stereotactic Body Radiation Therapy

As mention in the section 1.5; an approach utilizing established doses of fractionated SBRT (5 fractions of 8-10 Gy per fraction depending on site) (which are considered acceptable from a toxicity perspective) in combination with immune-checkpoint inhibitors seems reasonable.

1.9 Overall Risk/Benefit Assessment

The combination of nivolumab and ipilimumab has encouraging anti-tumor activity (durable responses and stable disease) in a Phase 1 study for subjects with mRCC. Given the potential for the induction of non-redundant immune mechanism with dual checkpoint blockade of PD-1 and CTLA-4 in combination with SBRT, there exists an opportunity to further improve outcomes in mRCC. The immunostimulatory potential of SBRT may lead to enhance clinical activity in subjects also receiving nivolumab plus ipilimumab. As nivolumab, ipilimumab and SBRT have non-overlapping mechanisms of action; their combination may be associated with increased efficacy that outweighs the potential incremental increase in toxicity in first- or second-line mRCC setting.

We are hoping that the use of nivolumab plus ipilimumab in combination with SBRT to up to two metastatic lesions lead to greater clinical benefit than use the combination of nivolumab and ipilimumab alone without excessive toxicity.

INVESTIGATIONAL PLAN and PATIENT SELECTION

2.1 Study Design

This is a multi-institution, single-arm phase II study to determine the safety and efficacy of SBRT (up to 2 metastatic sites preferentially lung, mediastinum or bone in combination of nivolumab and ipilimumab in patients with metastatic RCC (with a clear-cell component and at least 1 measurable metastatic lesion that is not being irradiated). The primary endpoints are safety and tolerability as well as ORR of the combination of nivolumab plus ipilimumab with SBRT.

The study is planned based on a two-stage design that allows early termination for lack of efficacy. A safety run-in phase will be included comprising the first 6 patients at minimum to ensure that the combination of nivolumab plus ipilimumab and SBRT is safe. Then, we will determine whether the combination of nivolumab plus ipilimumab and SBRT yields a clinically compelling antitumor activity measured as ORR, and evaluate other endpoints including TTP, DOR, PFS, OS and local control of irradiated sites.

Safety Run-in phase

There is no previous experience with SBRT used concurrently with nivolumab and ipilimumab in this study population. **Therefore, to ensure that the combination is safe, the first six patients will be treated and observed for toxicity for 6 weeks after radiation before continuing with further accrual.** Therefore, six patients will be enrolled at the proposed dose of nivolumab and ipilimumab in combination with SBRT. If 4 out of the first 6 patients experience Grade 3/4 toxicity or a lower grade toxicity requiring immune suppressive therapy during the safety run-in observation period (6 weeks after completion of SBRT), enrollment will cease and the study will be halted until further safety analysis of the combination regimen can be performed. If less than 4 out of the first 6 patients experience Grade 3/4 toxicities or require steroids, we will proceed with additional accrual with this regimen.

Toxicity Event: \geq grade 3 adverse event (CTCAE v 4.0) with an attribution of possible, probable, or definite, as well as need for steroids/ immunosuppressive therapy and lower grade toxicity

Efficacy phase:

A minimax Simon two-stage design is planned with the maximum sample size of 25 (including the 6 in the safety run-in phase). A total of 15 patients will be entered in the first

stage. If 6 or less achieve an objective response, then the response data will be reviewed carefully and study termination will be discussed. If a number of patients have near partial responses or evolving tumor shrinkage the team may decide to continue with accrual to get a larger sample size. If 7 or more patients have an objective response, then the second stage will proceed automatically with additional 10 patients. If a total of 17 or more patients respond, we will conclude this regimen is promising and warrants further study.

2.2 Duration of Study

Enrollment in the run-in phase of the study is expected to take approximately 3-6 months. Enrollment in the efficacy phase of the study is expected to take approximately 18 additional mo. Subjects may discontinue from treatment because of disease progression, unacceptable toxicity, withdrawal of consent, or at the discretion of the investigator. The end of the trial will occur on the day of the last visit of the last subject.

2.3 Study Population

For entry into the study, the following criteria MUST be met.

2.3...1 Inclusion Criteria

Eligibility waivers are not permitted. Subjects must meet all of the inclusion and exclusion criteria to be registered to the study. Study treatment may not begin until a subject is registered

1) *Signed Written Informed Consent*

- Willing and able to provide informed consent

2) *Target Population*

- Histological confirmation of RCC with a clear-cell component
- Metastatic (AJCC Stage IV) RCC
- Prior adjuvant or neoadjuvant therapy for localized or locally advanced RCC is allowed provided recurrence occurred = or > 6 months after the last dose of the adjuvant or neoadjuvant therapy
- Any number of prior systemic treatment regimen in the advanced/metastatic setting is allowed (cytokine, anti-angiogenic, mTOR inhibitor or clinical trial) including previously untreated patients
- Karnofsky Performance Status (KPS) of at least 70%
- Life expectancy of at least 3 months
- At least 2 metastatic sites of which at least 1 must be measurable as per RECIST 1.1

- Archival Formalin-fixed paraffin-embedded (FFPE) tumor tissue must be available for correlative studies (Note: Fine Needle Aspiration [FNA] and bone metastases samples are not acceptable for submission)
- Patients with favorable, intermediate and poor risk categories will be eligible for the study. *Patients must be categorized according to favorable versus intermediate/poor risk status at registration. International Metastatic RCC Database Consortium (IMDC) must be used to determine prognostic factors (Appendix 1)*

2.3.2 Exclusion Criteria:

1) Target Disease Exceptions

- Subjects with previously treated brain or CNS metastases are eligible provided that the subject has recovered from any acute effects of radiotherapy and is not requiring steroids, and any whole brain radiation therapy was completed at least 4 weeks prior to study drug administration, or any stereotactic radiosurgery was completed at least 2 weeks prior to study drug administration. Liver metastases will not be included as part of the radiated lesions to be treated.

2) Medical History and Concurrent Diseases

- Prior treatment with an anti-PD-1, anti-PD-L1, anti-PD-L2, anti-CD137, or anti-CTLA-4 antibody, or any other antibody or drug specifically targeting T-cell co-stimulation or checkpoint pathways. Prior treatment with HD IL-2 is allowed.
- Any active or recent history of a known or suspected autoimmune disease or recent history of a syndrome that required systemic corticosteroids (> 10 mg daily prednisone equivalent) or immunosuppressive medications except for syndromes which would not be expected to recur in the absence of an external trigger. Subjects with vitiligo or type I diabetes mellitus or residual hypothyroidism due to autoimmune thyroiditis only requiring hormone replacement are permitted to enroll. Patients with psoriasis not requiring active, systemic treatment are allowed.
- Any condition requiring systemic treatment with corticosteroids (> 10 mg daily prednisone equivalents) or other immunosuppressive medications within 14 days prior to first dose of study drug. Inhaled steroids and adrenal replacement steroid doses up to 10 mg daily prednisone equivalents are permitted in the absence of active autoimmune disease

- Uncontrolled adrenal insufficiency
- *Requirement for anti-coagulation with Coumadin, low molecular weight heparin and anti-thrombin inhibitors will be accepted if anticoagulation has been stable for at least 4 weeks and no recent history of prior bleeding complications.*
- Prior malignancy active within the previous 3 years except for locally curable cancers that have been apparently cured such as basal or squamous cell skin cancer, superficial bladder cancer, or carcinoma in situ of the cervix, breast or low risk Gleason 6 prostate cancer
- Known history of testing positive for human immunodeficiency virus (HIV) or known acquired immunodeficiency syndrome (AIDS)
- Any positive test for hepatitis B or hepatitis C virus indicating acute or chronic infection
- Known medical condition (eg, a condition associated with diarrhea or acute diverticulitis) that, in the investigator's opinion, would increase the risk associated with study participation or study drug administration or interfere with the interpretation of safety results
- Major surgery (eg, nephrectomy) less than 28 days prior to the first dose of study drug
- Anti-cancer therapy less than 14 days prior to the first dose of study drug or palliative, focal radiation therapy less than 14 days prior to the first dose of study drug
- Presence of any toxicities attributed to prior anti-cancer therapy, other than alopecia, that have not resolved to Grade 1 (NCI CTCAE v4) or baseline before administration of study drug

3) Physical and Laboratory Test Findings

- Any of the following laboratory test findings:
 - WBC < 2,000/mm³
 - Neutrophils < 1,500/mm³
 - Platelets < 100,000/mm³
 - AST or ALT > 3 x ULN (> 5 x ULN if liver metastases are present)
 - Total Bilirubin > 1.5 x ULN (except subjects with Gilbert Syndrome, who can have total bilirubin < 3.0 mg/dL)
 - Serum creatinine > 1.5 x upper limit of normal (ULN) or creatinine clearance < 40 mL/min (measured or calculated by Cockroft-Gault formula)

4) Allergies and Adverse Drug Reaction

- History of severe hypersensitivity reaction to any monoclonal antibody or study drug components

5) ***Other Exclusion Criteria***

- Prisoners or subjects who are involuntarily incarcerated
- Not suitable for SBRT treatment
- Subjects who are compulsorily detained for treatment of either a psychiatric or physical illness

2.3.3. Age and Reproductive Status

Women of childbearing potential (WOCBP) is defined as any female who has experienced menarche and who has not undergone surgical sterilization (hysterectomy or bilateral oophorectomy) or who is not postmenopausal. Menopause is defined clinically as 12 months of amenorrhea in a woman over 45 in the absence of other biological or physiological causes. In addition, women under the age of 62 must have a documented serum follicle stimulating hormone (FSH) level less than 40 mIU/mL.

Women of childbearing potential (WOCBP) receiving nivolumab will be instructed to adhere to contraception for a period of 23 weeks after the last dose of investigational product. Men receiving nivolumab and who are sexually active with WOCBP will be instructed to adhere to contraception for a period of 31 weeks after the last dose of investigational product. These durations have been calculated using the upper limit of the half-life for nivolumab (25 days) and are based on the protocol requirement that WOCBP use contraception for 5 half-lives plus 30 days and men who are sexually active with WOCBP use contraception for 5 half-lives plus 90 days.

Highly effective methods of contraception include:

- Male condoms with spermicide
- Hormonal methods of contraception including combined oral contraceptive pills, vaginal ring, injectables, implants and intrauterine devices (IUDs) such as Mirena® by WOCBP subject or male subject's WOCBP partner Female partners of male subjects participating in the study may use hormone based contraceptives as one of the acceptable methods of contraception since they will not be receiving study drug
- Nonhormonal IUDs, such as ParaGard®

- Tubal ligation
- Vasectomy
- Complete Abstinence*

*Complete abstinence is defined as complete avoidance of heterosexual intercourse and is an acceptable form of contraception for all study drugs. Subjects who choose complete abstinence are not required to use a second method of contraception, but female subjects must continue to have pregnancy tests. Acceptable alternate methods of highly effective contraception must be discussed in the event that the subject chooses to forego complete abstinence.

Less effective methods of contraception include:

- Diaphragm with spermicide
- Cervical cap with spermicide
- Vaginal sponge
- Male Condom without spermicide
- Progestin only pills by WOCBP subject or male subject's WOCBP partner
- Female Condom*.

*A male and female condom must not be used together

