4 STUDY ASSESSMENTS AND PROCEDURES

4.1 Flow Chart/Time and Events Schedule

Procedure	Screening Visit	Notes
Eligibility Assessment		
Informed Consent	X	
Inclusion/Exclusion Criteria	X	All inclusion/exclusion criteria should be assessed prior to treatment
Medical History	X	
Candidate for SBRT as assessed by Radiation Oncology	X	
Tumor Tissue	X	Patient must have lesion which is not radiated and accessible for core biopsies
Safety Assessment		
Physical Examination	X	
Vital Signs and Oxygen Saturation	X	Including BP, HR, & temperature. Obtain at the screening visit and within 72 hours prior to first dose
Physical Measurements (including Performance Status)	X	Height and weight and Karnofsky Performance Status
ECG	X	Within 28 days prior to treatment
Assessment of Signs and Symptoms	X	Within 28 days prior to treatment
Concomitant Medication Collection	X	Within 28 days prior to treatment
Laboratory Test	X	CBC w/differential, Chemistry panel including:

		LDH, AST, ALT, ALP, T.Bili, BUN or serum urea level, creatinine, Ca, albumin, Mg, Na, K, Cl, glucose, amylase, lipase, TSH, Free T4, Free T3, Hep B/C(HBV sAG, HCV antibody or HCV RNA), within 28 days prior to treatment. Within 72 hrs prior to re-dosing to include CBC w/ differential, LFTs, BUN or serum urea level, creatinine, Ca, Mg, Na, K, Cl, LDH, Glucose, amylase, lipase, TSH (with reflexive Free T4 and Free T3), FSH(women under 62)
Pregnancy Test (WOCBP only)	X	Within 28 days prior to treatment. A serum or urine pregnancy testing is required within 24 hrs of study treatment then every 4 weeks. [more frequently if required by local standard]. After discontinuation from nivolumab these should be repeated at approximately 30 days and approximately 70 days [or more frequently if required by local standard].
Efficacy Assessment		
Screening/Baseline Tumor Assessments	X	CT with contrast of the chest, abdomen, pelvis and all known sites of disease (or CT Chest w/o contrast and MRI of abdomen with or without contrast if reduced GFR or allergy). MRI (preferred) or CT scan of the Brain if known history of brain involvement.
Exploratory Biomarker Testing		
Research Biopsy*	X	Within 28 days prior to treatment (optional) and during week 7 on therapy (optional)
Blood Sample	X	Within 28 days prior to treatment and during week 7 on therapy

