4.2 Initial Registration

Eligible patients will be registered on study centrally at UT Southwestern Medical by the Lead Site Study Coordinator.

To register a patient, the following documents must be completed and emailed at [contact] M—F 8am to 5pm CST.

- Signed/dated patient consent form
- Eligibility checklist
- Copies of pre hormone therapy/chemotherapy or radiation therapy
- Screening labs(including pregnancy test)/vital signs and EKG
- CT reports
- Other materials may also be sent if considered pertinent for confirming patient eligibility, e.g. CT/MRI of C/A/P

The Lead Center will review the documents to confirm eligibility. To complete the registration process the Lead Center will:

- Assign a patient study number
- Patients found to be ineligible for participation after being consented will be considered screen failures, and documented as such in the Screening and Enrollment Log
- New subjects will receive a number beginning with 001 upon study consent such that the first subject consented is numbered 001, the second subject consented receives the number 002, etc.
- Upon confirmation of eligibility and enrollment as per the afore-mentioned instructions, the subject will be assigned a secondary number in the order of enrollment. For example, subject 001 will become 001-01 upon enrollment. If subject 002 screen fails, and subject 003 is the next subject enrolled, subject 003 will become 003-02 and so-on.
- For UTSW, each newly consented subject should be numbered using the schema provided above. Upon registration, the registrar will assign the additional registration/randomization code according to the numbering schema outlined above, which should then be entered as the patient study id in Velos upon updating the status to enrolled.

- The numbering schema should clearly identify the site number; the sequential number of the subject enrolled as well as the status of the subjects enrolled so that the number of subjects consented versus the number of subjects actually enrolled may be easily identified.

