 d. Ipilimumab is to be administered as an approximately 30-minute IV infusion. When both study drugs are to be administered on the same day, separate infusion bags and filters must be used for each infusion. Nivolumab is to be administered first.
 e. SBRT (5 fractions of 10 Gy) is to be delivered anytime between Day 1 of Week 1 (Cycle 1) and Day 1 of Week 4 (Cycle 1) of the nivolumab and ipilimumab combination dosing (within the first 3 weeks after the initiation of nivolumab and ipilimumab). SBRT is preferred to be delivered in the first 2 weeks.
 f. Temp, Pulse, B.P., Weight
 g. Karnofsky Performance Status
 h. Oxygen saturation by pulse oximetry should be obtained prior to dosing (at rest and with exertion) Also perform if any new or worsening pulmonary symptoms present
 i. CT with contrast of the chest, abdomen, pelvis and all known sites of disease (or CT Chest w/o contrast and MRI of abdomen with or without contrast if reduced GFR or allergy). MRI (preferred) or CT scan of the Brain if known history of brain involvement (all known sites of disease should be assessed at baseline)
 j. CBC w/differential and platelets
 k. Full Chemistry Panel including: LDH, AST, ALT, ALP, T.Bili, BUN, creatinine, Ca+, Mg+, Na-, K+, HCO3-, Cl-, glucose, albumin, T.Protein, amylase, lipase
 l. WOCBP only (serum or urine) at screening and within 24 hours of dosing
 m. HepB sAg & HCV Ab or HCV RNA
 n. Multiple tumor biopsies – pre-treatment (optional), at week 7 of treatment (optional) and at the time of progression (optional)
 o. Blood samples will be collected for research at pre-treatment, at week 7 of treatment and at the time of progression
 p. Prior to entry into the protocol, all patients need to be discussed with [name] (JHU), [name] (UTSW) or co-investigator Radiation Oncologist from the Radiation Therapy Department to determine eligibility/feasibility for SBRT. The cancer lesion(s) to be radiated should be determined by the Radiation Oncologist in collaboration with the Principal Investigator/Medical Oncologist
 q. Cycle 1 Day 1 labs do not need to be performed if done \leq 72 hours of dosing as part of the Day -3 to +1 labs
 r. Perform 30 days \pm 1 week from last dose of study drug

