4.4 Safety Assessments / Considerations

At baseline, a medical history will be obtained to capture relevant underlying conditions. The baseline examinations should include weight, height, Karnofsky Performance Status, BP, HR, and temperature. Baseline signs and symptoms are those that are assessed within 28 days prior to treatment. Concomitant medications will be collected from within 28 days prior to treatment.

Baseline local laboratory assessments should be done within 28 days prior to treatment to include: CBC w/differential, LFTs (ALT, AST, total bilirubin, alkaline phosphatase), BUN or serum urea level, creatinine, Ca, albumin, Mg, Na, K, Cl, LDH, glucose, amylase, lipase, TSH, Free T4, Free T3, and Hep B and C testing (HBV sAg, HCV Ab or HCV RNA).

Pregnancy testing for WOCBP must be performed within 24 hours prior to the initial administration of study drug at baseline and then every 4 weeks during the treatment period and at the safety follow-up visits. After discontinuation from nivolumab these should be repeated at approximately 30 days and approximately 70 days [or more frequently if required by local standard]. If, following initiation of the investigational product, it is subsequently discovered that a study **subject is pregnant or may have been pregnant** at the time of investigational product exposure, including during at least 6 half lives after product administration, the investigational product will be permanently discontinued in an appropriate manner (eg, dose tapering if necessary for subject safety). The investigator must immediately notify Worldwide Safety @BMS of this event via the Pregnancy Surveillance Form in accordance with SAE reporting procedures. Follow-up information regarding the course of the pregnancy, including perinatal and neonatal outcome and, where applicable, offspring information must be reported on the Pregnancy Surveillance Form [provided upon request from BMS]. Any pregnancy that occurs in a female partner of a male study participant should be reported to BMS. Information on this pregnancy will be collected on the Pregnancy Surveillance Form.

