On study local laboratory assessments should be done within 72 hours of dosing to include; CBC w/differential, LFTs (ALT, AST, total bilirubin, alkaline phosphatase), BUN or serum urea level, creatinine, Ca, Mg, Na, K, Cl, LDH, glucose, amylase, lipase, TSH with reflexive Free T4, Free T3 on Day 1 of Weeks 1 and 4 for Cycles 1 and 2 and on Day 1 of Weeks 1 and 5 starting from Cycle 3. Additional measures including non-study required laboratory tests should be performed as clinically indicated or to comply with local regulations. Laboratory toxicities (eg, suspected drug induced liver enzyme elevations) will be monitored during the follow-up phase via on site/local labs until all study drug related toxicities resolve, return to baseline or are deemed irreversible. In addition, LFTs should also be assessed prior to the second dose of each cycle. The results of these labs should be reviewed prior to dosing. Amylase, Lipase and thyroid tests must be drawn, but do not need to be resulted prior to infusion unless patient is symptomatic. The following laboratory abnormalities should be documented and reported appropriately:

- any laboratory test result that is clinically significant or meets the definition of an SAE
- any laboratory abnormality that required the subject to have study drug discontinued or interrupted
- any laboratory abnormality that required the subject to receive specific corrective therapy.

Oxygen saturation by pulse oximetry should be obtained prior to each dosing and at any time a subject has any new or worsening respiratory symptoms. A reading at rest

and on exertion should be obtained at each time point. The extent of the exertion should be based on the judgment of the investigator, but should remain consistent for each individual subject throughout the study. If the patient's status changes, the investigator can alter the extent of exertion based on their medical judgment. If a subject shows changes on pulse oximetry or other pulmonary related signs (hypoxia, fever) or symptoms (eg, dyspnea, cough, fever) consistent with possible pulmonary adverse events, the patient subject should be immediately evaluated to rule out **pulmonary toxicity**. An algorithm for the management of suspected pulmonary toxicity can be found in the appendix of the nivolumab Investigator's Brochure.

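### Section 2.3.3 reverses the FSH check on menopause: women under 62 need a value below 40 mIU/mL, although FSH rises after menopause

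*Combined protocol and SAP*

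**What the plan says.** Section 2.3.3 describes a WOCBP as a female past menarche "who has not undergone surgical sterilization (hysterectomy or bilateral oophorectomy) or who is not postmenopausal". It then defines menopause: "Menopause is defined clinically as 12 months of amenorrhea in a woman over 45 in the absence of other biological or physiological causes". The next sentence, introduced as an addition to that definition, says that "women under the age of 62 must have a documented serum follicle stimulating hormone (FSH) level less than 40 mIU/mL".

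WOCBP status controls several protections:

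- **Pregnancy tests around dosing.** Section 4.3, footnote l: "WOCBP only (serum or urine) at screening and within 24 hours of dosing".
- **Repeat tests.** Sections 4.1 and 4.4 ask for a test every 4 weeks on treatment and again at about 30 and 70 days after nivolumab ends.
- **Contraception.** Section 2.3.3 sets 23 weeks after the last dose.

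FSH appears in one other place, the laboratory row of Section 4.1, in the list drawn within 72 hours before re-dosing: "TSH (with reflexive Free T4 and Free T3), FSH(women under 62". No cut-off is given there. The inclusion and exclusion criteria contain no FSH or pregnancy criterion.

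**The concern.** Loss of ovarian function raises FSH. A low value in a woman with 12 months of amenorrhea is therefore a reason to doubt that she is postmenopausal. The FSH step exists to catch the woman whose amenorrhea is not true menopause, and with the inequality reversed it releases that woman from the precautions and holds back the one whose menopause the test supports.

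The safety stake is fetal exposure to two checkpoint antibodies, with nivolumab continuing for up to two years. The opposite error, treating a postmenopausal woman as WOCBP, is a burden and not a hazard.

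**Working it through.** There is no power or error-rate figure to reproduce. The check applies the written rule to cases and then bounds the consequence.

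**1. Is the direction really reversed?** The comparison is printed in words, so it is not a symbol lost in PDF conversion. Its position, directly after the menopause definition and joined as a further condition, makes it a requirement for calling a woman under 62 postmenopausal.

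**2. Who reaches the FSH step?** Unsterilised women over 45 and under 62 (46 to 61 in whole years) with at least 12 months of otherwise unexplained amenorrhea. Menstruating women, women of 45 or younger, women of 62 or older and sterilised women are not affected.

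**3. Worked cases, reading WOCBP as not sterilised *and* not postmenopausal:**

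| Amenorrheic, unsterilised woman | Rule as written | Rule with FSH above 40 |
|---|---|---|
| Age 47, FSH 8 mIU/mL | postmenopausal, exempt | WOCBP |
| Age 55, FSH 70 mIU/mL | WOCBP | postmenopausal, exempt |

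**4. Do other readings rescue the text?**

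- *Taking the printed 'or' literally.* Every unsterilised woman past menarche is then WOCBP, and the menopause and FSH sentences have no function. This is safe but plainly not intended.
- *FSH sentence as a description of WOCBP.* Its position does not support this.
- *FSH sentence as an entry criterion.* Women under 62 with high FSH would be barred from the trial, which nothing else in the protocol suggests.

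**5. What does a wrongly exempted woman lose over 2 years (104 weeks)?**

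- Four-weekly tests: 104 / 4 = 26.
- Post-treatment tests: 2 (about 30 and 70 days).
- Contraception: Section 2.3.3 derives its period from 5 half-lives of 25 days plus 30 days, which is 5 × 25 + 30 = 155 days, or 155 / 7 = 22.1 weeks; the protocol uses 23. Adding the treatment period gives 104 + 23 = 127 weeks.

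The Section 4.3 calendar gives slightly higher counts. Doses at Weeks 1, 4, 7 and 10, then every 4 weeks from Week 13 to Week 101, make 4 + 23 = 27 dosing-day tests. The calendar also marks testing at visits X1, X2 and X3, which is 3 post-treatment tests.

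**6. How many women?** The documents give no sex, age or FSH distribution, so the shares below are assumptions.

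| Quantity | Low | High |
|---|---|---|
| Reaching the FSH step (20–40% women, 15–45% of them eligible for it) | 25 × 0.20 × 0.15 = 0.75 | 25 × 0.40 × 0.45 = 4.5 |
| Wrongly exempted (5–20% have FSH below 40) | 0.75 × 0.05 = 0.04 | 4.5 × 0.20 = 0.9 |
| Wrongly treated as WOCBP (the other 80–95%) | 0.75 × 0.80 = 0.6 | 4.5 × 0.95 = 4.3 |

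**7. Where is FSH scheduled?** The 28-day list in Section 4.1, calendar footnote k, the Section 4.4 baseline list ("glucose, amylase, lipase, TSH, Free T4, Free T3, and Hep B and C testing") and its on-study list ("TSH with reflexive Free T4, Free T3 on Day 1 of Weeks 1 and 4 for Cycles 1 and 2") all omit it. This gap fails safe: without a documented FSH a woman stays WOCBP and is tested. The 72-hour draw may also cover the first dose, because the on-study list includes Week 1 of Cycle 1.

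**The case against.** The strongest reply is that the harm depends on reading one word generously and another strictly. Taken literally, the 'or' in the WOCBP definition keeps every unsterilised woman under testing and contraception. If staff are trusted to see past that 'or', they may equally see what the FSH test is for. This makes the practical misclassification conditional, and that part stands. It does not make the text acceptable: on one reading the FSH rule does nothing, and on the other it works backwards. Section 8.1 requires the study to be run as the protocol describes, so staff should not have to choose between a wrong rule and a deviation.

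The amenorrhea condition also limits the risk. The reversed test exempts no woman whom the clinical definition alone would not have exempted, so what is lost is a second check. A woman wrongly exempted is not thereby known to be fertile. That is correct.

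A pregnancy test may still be done once, because the Section 4.2 registration packet asks for "Screening labs(including pregnancy test)/vital signs and EKG" without limiting it to WOCBP. One test at entry does not replace repeat testing or contraception.

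Finally, the head counts rest on assumed shares and support no more than 'few', and the 104 on-treatment weeks of contraception are inferred, since Section 2.3.3 states only the 23 weeks after the last dose. Both limits are accepted.

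**Conclusion.** The concern holds. The FSH criterion in Section 2.3.3 points the wrong way, and nothing elsewhere in the protocol corrects it. The conclusion needs only the printed wording and the fact that FSH rises after menopause.

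The consequence depends on the evident reading of the WOCBP definition and is confined to unsterilised, amenorrheic women aged 46 to 61. Under the stated assumptions fewer than one woman in a trial of 25 would be wrongly exempted (0.04 to 0.9), and 0.6 to 4.3 would be tested and asked to use contraception unnecessarily. This is a participant-safety error that should be fixed. It has no bearing on the ORR analysis, the sample size or the stopping rules.

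**What to change.** Make two corrections in Section 2.3.3:

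1. In the FSH sentence, replace 'less than' with 'greater than' 40 mIU/mL, and state that the test serves to confirm menopause.
2. In the WOCBP definition, replace the 'or' before the postmenopausal clause with 'and'.

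As a clarification only, list FSH for women under 62 who claim postmenopausal status with the 28-day screening laboratory tests in Sections 4.1, 4.3 and 4.4, and state that a woman without a documented FSH is treated as WOCBP.

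The cost is two short wording changes in an amendment. FSH is already a protocol test and can be taken with an existing screening draw, so no visit is added.
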